8 CLINICAL MONITORING

The Sponsor or designee has ethical, legal and scientific obligations to carefully follow this study in accordance with established research principles and applicable regulations. The investigator, as part of his responsibilities, is expected to cooperate with the Sponsor or designee in ensuring that the study adheres to the protocol and GCP requirements.

As part of a concerted effort to fulfill these obligations, monitoring will be carried out during the study in accordance with the Monitoring Plan set forth for this trial.

9 STATISTICAL CONSIDERATIONS

9.1 STATISTICAL AND ANALYTICAL PLANS

All statistical analysis will be “intent-to-treat”, with each patient being considered as part of their randomized group irrespective of the actual treatment received. Patients not having an event, or lost to follow-up will be censored at the time of their last documented follow-up visit or phone call.

The study is designed to demonstrate the non-inferiority of the WATCHMAN device compared to the control group, with regards to the primary endpoint (composite of all-cause mortality, stroke (ischemic and hemorrhagic), or bleeding (major and/or life-threatening)). Non-inferiority will be assessed using the 1-sided 97.5% confidence interval around the hazard ratio (WATCHMAN-TAVR: TAVR only). Non-inferiority will be demonstrated if the 1-sided 97.5% upper confidence limit for the difference in proportions is less than 1.5. If the non-inferiority objective is met, additional analyses to assess superiority of the WATCHMAN group to the control group will be performed. The composite primary endpoint will also be summarized as events per 100 patient-years of follow-up.

For data collected at baseline, during the procedure and at follow-up, descriptive statistics will be generated. Continuous variables will be summarized with reporting of mean, standard deviation (SD), median, interquartile range (Q1, Q3) and range (minimum and maximum). General linear models will be used to compare continuous variables across treatment groups. Categorical variables will be summarized using counts and percentage of subjects and compared using the standard Chi-square statistic or Fisher’s Exact test, as appropriate.

In general, missing data will not be imputed and will remain missing, unless otherwise indicated.

9.2 STATISTICAL HYPOTHESES

The study is designed to demonstrate the non-inferiority of the WATCHMAN device compared to the control group, with regards to the primary endpoint (composite of all-cause mortality, stroke (ischemic and hemorrhagic), bleeding (major and/or life-threatening)).

The following null hypotheses will be tested:

- H_{01} : The hazard ratio for WATCHMAN + TAVR relative to TAVR is ≥ 1.5 (non-inferiority)
- H_{02} : The hazard ratio for WATCHMAN + TAVR relative to TAVR is ≥ 1.0 (superiority)

If H_{01} is rejected, then H_{02} will also be tested. If the null hypothesis for non-inferiority is not rejected, H_{02} will not be tested.

9.3 ANALYSIS POPULATIONS

Intention-to-Treat Population (ITT): The primary analysis will be based on the ITT population. All randomized subjects will be analyzed according to their original randomization assignment (WATCHMAN+TAVR or TAVR) regardless of treatment received.

Per-protocol population: The per-protocol population is defined as patients in the WATCHMAN groups who received both the WATCHMAN and the prosthetic valve. In the TAVR only group, it is defined as patients who had the prosthetic valve placed.

9.4 DESCRIPTION OF STATISTICAL METHODS

9.4.1 GENERAL APPROACH

The ITT population will be used to analyze the primary and secondary endpoints. The non-inferiority hypothesis will only be tested using the primary endpoint of all-cause mortality, stroke, and major/life-threatening bleeding. Event rates, hazard ratio and 95% confidence intervals and a p-value associated with the non-inferiority hypothesis will be provided. If the non-inferiority objective is met, a p-value for the superiority hypothesis will also be provided. Secondary endpoints will be summarized using event rates, hazard ratios and 95% confidence intervals. Nominal p-values for comparisons between treatment groups will be provided for descriptive purposes only.

All patients should be followed until the termination of the study, regardless of adherence to the treatment strategy. Available information on patients lost to follow-up will be included in the analyses. Patients not reaching a primary endpoint by the time of study termination will be censored at their last known assessment.

Statistical methods will be further outlined in the Statistical Analysis Plan (SAP).

9.4.2 ANALYSIS OF THE PRIMARY ENDPOINT

The primary endpoint is the first occurrence of all-cause mortality, stroke or major/life-threatening bleeding event within one year following randomization. Estimates of the hazard ratio and 95% confidence intervals will be based on the Cox proportional hazards model, under the assumption of proportional hazards. Comparison of cumulative hazard functions will be based on the log-rank test.

The upper bound of the confidence interval will be generated from the Cox proportional hazards model with treatment group as a factor.

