9.4.4 SAMPLE SIZE

The WATCH-TAVR is a randomized, prospective multi-center event-driven non-inferiority study to determine the safety and efficacy of the WATCHMAN device in patients with non-valvular AF undergoing TAVR for aortic stenosis. The control group consists of patients undergoing TAVR who are on standard medical practice, with oral anticoagulation at the discretion of the treating physician. The treatment group will have the WATCHMAN implantation procedure performed simultaneously with TAVR. The primary endpoint is a composite of all-cause mortality, stroke, life-threatening or major bleeding. The objective of the study is to demonstrate non-inferiority of the TAVR plus WATCHMAN device compared to the TAVR only group.

Data from the PARTNER¹ trial, along with the SOURCE-XT¹⁰ and FRANCE-2¹¹ registries show all-cause mortality rates in TAVR patients with AF vary from 19-30%, stroke rates from 6-10% and major/life-threatening bleeding from 17-22%. The PROTECT-AF trial for the WATCHMAN device in non-valvular atrial fibrillation patients reported a risk reduction of nearly 40% for the primary composite endpoint of stroke, systemic embolization or cardiovascular or unexplained death (RR 0.61, 95%CrI 0.42-1.07)⁴.

The following assumptions were used to determine the sample size needed to assess the non-inferiority hypothesis for the composite primary endpoint of all-cause mortality, stroke or major or life-threatening bleeding:

- One-sided $\alpha = 0.025$
- Primary event rate in the control population (TAVR only) of 35% at one year
- Non-inferiority margin of 1.5
- Underlying hazard ratio of active to control is 1.0
- Power at least 80%
- Lost to follow-up rate 10%

Assuming level of significance (α) to be 0.05 (or $\alpha = 0.025$ one-sided) and aiming for a study power ($1 - \beta$) of 80%, we estimate 191 primary events will be needed to rule out an upper limit of the one-sided 97.5% confidence interval of 1.5. Assuming an enrollment duration of 18 months, follow-up period of 24 months, and 10% drop out rate per annum, the minimum total sample size required is 350 (175 per group).

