5.2 Analysis Populations

Intention-to-Treat Population (ITT):

The primary analysis will be based on the ITT population. All randomized subjects will be analyzed according to their original randomization assignment (WATCHMAN+TAVR or TAVR) regardless of treatment received. The ITT analysis will be censored at 2 years (730 days) after randomization.

Per-protocol population (PP):

The per-protocol population is defined as patients in the WATCHMAN groups who received both the WATCHMAN and the prosthetic valve. In the TAVR only group, it is defined as patients who had the prosthetic valve placed. The PP analysis will be censored at 2 years (730 days) after randomization.

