7 ANALYSES

7.1 Primary Analysis

The ITT analysis will include all positively adjudicated post-randomization primary endpoints within the ITT analysis set through 24 months (730 days) after randomization.

The study is designed to demonstrate the non-inferiority of the WATCHMAN device compared to the control group, with regards to the primary endpoint (composite of all-cause mortality, stroke (ischemic and hemorrhagic), or bleeding (major and/or life-threatening)). Non-inferiority will be assessed using the 1-sided 97.5% confidence interval around the hazard ratio (WATCHMAN-TAVR: TAVR only). Non-inferiority will be demonstrated if the 1-sided 97.5% upper confidence limit for the difference in proportions is less than 1.5. If the non-inferiority objective is met, additional analyses to assess superiority of the WATCHMAN group to the control group will be performed. The composite primary endpoint will also be summarized as events per 100 patient-years of follow-up.

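### The protocol limits the primary endpoint to one year while the SAP counts events to 730 days, and a one-year window cannot supply the planned 191 events or 80% power

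*Protocol*

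**What the plan says.** The only primary-endpoint time limit in the protocol is in section 9.4.2: "The primary endpoint is the first occurrence of all-cause mortality, stroke or major/life-threatening bleeding event within one year following randomization". Elsewhere the protocol does not support that limit. Sections 3.2 and 9.2 give the composite with no window, 9.4.1 censors event-free patients at their last assessment before the study ends, and 9.4.4 sizes the trial on 24 months of follow-up.

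The SAP uses two years. Section 7.1 includes adjudicated "primary endpoints within the ITT analysis set through 24 months (730 days) after randomization". Section 5.2 adds: "The ITT analysis will be censored at 2 years (730 days) after randomization". Section 5.4.2 applies the same 730-day cap to the time-to-event variable. SAP 2.2.1 repeats the protocol's definition but drops the one-year limit and puts nothing in its place.

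Both documents tie the trial to an event count. In Protocol 9.4.4, "we estimate 191 primary events will be needed to rule out an upper limit of the one-sided 97.5% confidence interval of 1.5", to be drawn from about 350 patients. SAP 5.1 triggers the final analysis at 191 events, or at an administrative stop.

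**The concern.** The window determines which events enter the only confirmatory test, and the superiority test is gated on that result (Protocol 9.2). The two windows could give different answers. The device arm carries added implant risk at the outset and early warfarin plus aspirin, whereas the expected gain, less bleeding from long-term anticoagulation, builds up later (Protocol 1.3.1, 1.3.2 and 6.2.4). The hazard ratio over one year may therefore differ from that over two.

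No blinding is described, so the window should be fixed beyond dispute before results are seen. As written, a reader holding the protocol could fairly call the 730-day analysis a changed primary endpoint. If the protocol's wording were followed instead, the trial would be well short of its stated power.

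**Working it through.** **Inputs**, from Protocol 9.4.4, repeated in SAP 4:
- One-sided alpha 0.025, power 80%; under Protocol 9.1, "Non-inferiority will be assessed using the 1-sided 97.5% confidence interval around the hazard ratio".
- "Non-inferiority margin of 1.5"; "Underlying hazard ratio of active to control is 1.0".
- Control risk 35% at one year; 350 patients, 1:1.
- Drop-out 10% per annum in the text; the list of assumptions gives 10% with no time unit.

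**Step 1: the plan's event count.** By Schoenfeld's formula, D = 4(z₀.₉₇₅ + z₀.₈₀)² / (ln 1.5)² = 4(1.9600 + 0.8416)² / 0.1644 = 190.97, which rounds up to 191. This matches the plan exactly.

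**Step 2: event probability.** With constant hazards, λ = −ln(0.65) = 0.4308 per year for events and η = −ln(0.90) = 0.1054 per year for drop-out. The probability of an observed event by time T is

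P(T) = λ/(λ+η) × [1 − exp(−(λ+η)T)],

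the same in both arms because the assumed hazard ratio is 1.0.

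- One year: 0.4308/0.5361 × (1 − e^(−0.5361)) = 0.3334, so 350 × 0.3334 = 116.7 events. Without drop-out: 350 × 0.35 = 122.5.
- Two years: 0.4308/0.5361 × (1 − e^(−1.0723)) = 0.5285, so 185.0 events. Without drop-out: 350 × (1 − 0.65²) = 202.1.

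**Step 3: power.** Power = Φ(½√D × ln 1.5 − 1.96). At D = 122.5 this is Φ(2.244 − 1.960) = Φ(0.284) = 61.2%.

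| Window | Drop-out | P(event) | Events from 350 | Power | N for 191 events |
|---|---|---|---|---|---|
| 1 year | none | 0.3500 | 122.5 | 61.2% | 546 |
| 1 year | 10% per year | 0.3334 | 116.7 | 59.1% | 573 |
| 1 year | 10% contribute nothing | 0.3150 | 110.3 | 56.7% | 607 |
| 2 years | none | 0.5775 | 202.1 | 82.2% | 331 |
| 2 years | 10% over two years | 0.5522 | 193.3 | 80.5% | 346 |
| 2 years | 10% per year | 0.5285 | 185.0 | 78.7% | 362 |

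The plan's 350 lies between 346 and 362, so it was evidently sized on a two-year window.

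**Step 4: can a one-year window reach 191?** That would need an overall one-year risk of 191/350 = 54.6% with no drop-out, against the planned 35%. The binomial standard deviation of the one-year count is √(350 × 0.35 × 0.65) = 8.9, so 191 lies (191 − 122.5)/8.9 = 7.7 standard deviations above expectation. In 4,000 simulated trials with the one-year window and 10% annual drop-out, the mean count was 116.7, power was 57.6% and none reached 191 events.

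**The case against.** The best defence is that the intention is clear. One phrase in Protocol 9.4.2 stands against the rest of the protocol and three sections of the SAP. Protocol 9.4.1 says the SAP will develop the methods further, and the SAP cites protocol v4.4. On that reading the power shortfall belongs to an analysis nobody plans to run, and the 191 and 350 are sound.

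Much of this is right: 191 and 350 are not in error, and two years is the better-supported reading. But a promise of further detail in the SAP is not a rule of precedence. It does not cover doubling the endpoint window without saying so, and the SAP's own endpoint definition gives no window. Protocol 3.1 also leaves some doubt about intent. Its statement on WATCHMAN use in the TAVR-only arm covers only the first year, and visits beyond one year may be by telephone.

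Two qualifications stand. The 191-event trigger is unreachable under the planning assumptions, not in logic, and SAP 5.1 keeps the administrative-stop route open. Also, the 730-day window is itself tight: at 10% drop-out per year it gives 185 expected events, slightly below target, with power of 78.7%.

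**Conclusion.** The concern holds and should be corrected before analysis. The documents give conflicting windows for the primary endpoint, and the one-year version is incompatible with the trial's own sizing. It falls about 70 events short (191 − 122.5 = 68.5 without drop-out; 191 − 116.7 = 74.3 with 10% per year) and has 59–61% power instead of 80%. The two-year version gives 185–202 events and 79–82% power, in line with the plan.

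The figure of 122.5 is simply 35% of 350 and needs no assumption about the shape of the hazard. The two-year counts assume a constant hazard. If events cluster around the procedure, with one-year risk still 35%, the two-year counts would be lower. All drop-out figures assume a constant drop-out rate, except the row in which 10% of patients contribute nothing.

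**What to change.** - In Protocol 9.4.2, replace the one-year limit with 24 months (730 days) from randomization, and state the same window in Protocol 3.2 and SAP 2.2.1.
- If a one-year result is wanted, list it as secondary and descriptive.
- Reconcile the first-year statement in Protocol 3.1 on WATCHMAN use in the TAVR-only arm with a two-year primary window. This review takes no position on what that clinical rule should be.
- If the sponsor did intend one year, wording alone will not do. The sample size must be re-derived (546 to 607 patients for 191 events, depending on drop-out), and the event trigger with it.

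Aligning on 730 days costs only an amendment to the wording of both documents. The 24-month contact is already in the schedule for both arms.

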9.4.3 ANALYSIS OF THE SECONDARY ENDPOINT(S)

Secondary endpoints will include the following:

- Time from randomization to each component of the primary endpoint:
 - All-cause mortality
 - Any stroke
 - Any occurrence of major or life-threatening bleeding (as per VARC2 definition of bleeding)

- Time to death from cardiovascular causes
- Time to ischemic stroke
- Time to hemorrhagic stroke
- Arterial or venous thrombosis or embolism
- Rehospitalization related to WATCHMAN procedure or WATCHMAN device.
- Procedural costs related to the initial TAVR procedure and WATCHMAN device implantation.

Analysis of time-to-event endpoints for the components will be analyzed similarly to that of the primary endpoint, except there will be no testing of the non-inferiority hypothesis. Point estimates and 95% confidence intervals will be derived from a Cox proportional model with treatment group as a factor. Descriptive frequencies of the endpoints and Kaplan-Meier curves will be presented. P-values may be provided for descriptive purposes, but should not be considered informative. The frequency of procedure related complications, device/implant failure or systemic embolism will be summarized with descriptive statistics.

Costs directly related to the initial TAVR procedure and WATCHMAN device implantation will be collected.

9.4.4 SAMPLE SIZE

The WATCH-TAVR is a randomized, prospective multi-center event-driven non-inferiority study to determine the safety and efficacy of the WATCHMAN device in patients with non-valvular AF undergoing TAVR for aortic stenosis. The control group consists of patients undergoing TAVR who are on standard medical practice, with oral anticoagulation at the discretion of the treating physician. The treatment group will have the WATCHMAN implantation procedure performed simultaneously with TAVR. The primary endpoint is a composite of all-cause mortality, stroke, life-threatening or major bleeding. The objective of the study is to demonstrate non-inferiority of the TAVR plus WATCHMAN device compared to the TAVR only group.

Data from the PARTNER¹ trial, along with the SOURCE-XT¹⁰ and FRANCE-2¹¹ registries show all-cause mortality rates in TAVR patients with AF vary from 19-30%, stroke rates from 6-10% and major/life-threatening bleeding from 17-22%. The PROTECT-AF trial for the WATCHMAN device in non-valvular atrial fibrillation patients reported a risk reduction of nearly 40% for the primary composite endpoint of stroke, systemic embolization or cardiovascular or unexplained death (RR 0.61, 95%CrI 0.42-1.07)⁴.

The following assumptions were used to determine the sample size needed to assess the non-inferiority hypothesis for the composite primary endpoint of all-cause mortality, stroke or major or life-threatening bleeding:

- One-sided $\alpha = 0.025$
- Primary event rate in the control population (TAVR only) of 35% at one year
- Non-inferiority margin of 1.5
- Underlying hazard ratio of active to control is 1.0
- Power at least 80%
- Lost to follow-up rate 10%

Assuming level of significance (α) to be 0.05 (or $\alpha = 0.025$ one-sided) and aiming for a study power ($1 - \beta$) of 80%, we estimate 191 primary events will be needed to rule out an upper limit of the one-sided 97.5% confidence interval of 1.5. Assuming an enrollment duration of 18 months, follow-up period of 24 months, and 10% drop out rate per annum, the minimum total sample size required is 350 (175 per group).

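### With 10% loss per annum and the SAP's 730-day cap, the stated minimum of 350 narrowly misses 191 expected events and 80% power (about 185 events, 79%)

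*Protocol*

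**What the plan says.** Protocol 9.4.4 lists the design inputs: one-sided alpha of 0.025, "Non-inferiority margin of 1.5", "Underlying hazard ratio of active to control is 1.0", "Primary event rate in the control population (TAVR only) of 35% at one year", "Power at least 80" per cent, and "Lost to follow-up rate 10" per cent. The loss bullet has no time unit.

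The closing paragraph of the same section gives 191 primary events. It then adds 18 months of enrollment, 24 months of follow-up and "10% drop out rate per annum, the minimum total sample size required is 350 (175 per group"). SAP 4 repeats the bullets and the closing paragraph.

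On the length of follow-up, Protocol 3.1 and the protocol summary give two years per patient. The SAP applies this as a hard limit: "The ITT analysis will be censored at 2 years (730 days) after randomization" (SAP 5.2, with the same limit in SAP 5.4.2 and 7.1). Protocol 9.4.1, in contrast, asks that patients be followed until the study terminates, and both documents call the trial event-driven. SAP 5.1 sets the final analysis at 191 events, or at an administrative stop.

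**The concern.** The number of patients needed for 191 events depends on the loss rate and on how long each patient can contribute events. The section gives the loss rate once with a unit and once without, and it does not say which follow-up calendar the calculation used. If loss is 10% per annum and nobody contributes events after day 730, 350 patients may be too few for the stated target.

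Two headline figures are at stake: the minimum of 350 and power of at least 80%. There is also a practical consequence. Under a 730-day cap events stop accruing once the last patient reaches two years, so an event-driven trial can end short of its trigger.

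**Working it through.** **Inputs.** Alpha, margin, true hazard ratio, control risk, power and loss come from Protocol 9.4.4. Allocation is 1:1 (Protocol 6.1.1). The two-year limit per patient comes from Protocol 3.1 and SAP 5.2. Two assumptions are ours: a constant event hazard, and loss acting as a competing exponential process. The documents state neither.

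**1. Events (the plan's own figure).** E = 4(1.960 + 0.8416)² / (ln 1.5)² = 4 × 7.849 / 0.1644 = 190.97, rounded up to 191. The plan's figure reproduces.

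**2. Hazards.** Events: λ = −ln(0.65) = 0.4308 per year, the same in both arms because the true hazard ratio is 1.0. Loss at 10% per annum: η = −ln(0.9) = 0.1054, or η = 0.10 if the rate is entered directly as a hazard.

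**3. Probability of an observed event within two years.** P = λ/(λ+η) × [1 − exp(−2(λ+η))].
- η = 0.1054: 0.8035 × (1 − 0.3422) = 0.5285, so 350 × 0.5285 = 185.0 events.
- η = 0.10: 0.8116 × (1 − 0.3459) = 0.5309, so 350 × 0.5309 = 185.8 events.

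**4. Power and N.** Power = Φ(√(E/4) × ln 1.5 − 1.960).
- 185.0 events: Φ(0.797) = 78.7%. N for 191 events = 191/0.5285 = 361.4, so 362.
- 185.8 events: Φ(0.803) = 78.9%. N = 191/0.5309 = 359.8, so 360.

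**5. Chance of reaching the trigger.** Treating the event count as binomial with 350 patients and these values of P, the chance of at least 191 events is about 28% (η = 0.1054) or 31% (η = 0.10).

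**6. Other readings of the same inputs.** Where follow-up ends at a common date, P is averaged over uniform 18-month accrual. Ranges cover the two conversions of the annual rate.

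| Reading | Events from 350 | Power | N for 191 events |
|---|---|---|---|
| 2 years per patient, 10% per annum | 185.0–185.8 | 78.7–78.9% | 360–362 |
| 2 years per patient, 10% in total over 24 months (η = 0.0527) | 193.3 | 80.5% | 346 |
| To 24 months after last entry, no cap, 10% per annum | 215.1–216.3 | 84.5–84.7% | 310–311 |
| As the row above, but 35% entered as an annual hazard of 0.35 | 190.6–191.7 | 79.9–80.2% | 349–351 |
| As the row above, but with the 730-day cap | 160.8–161.5 | 72.9–73.1% | 414–416 |
| Common close 24 months after first entry, 10% per annum | 133.4–133.9 | 64.9–65.0% | 500–501 |

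Two readings come close to 350. One takes 10% as the total loss over 24 months. The other takes 10% per annum, uncapped follow-up and 35% as a hazard. The second gives the closer match.

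**The case against.** The strongest reply is that the calculation was probably not built on exactly 24 months per patient. If it had been, the 18-month accrual would drop out and there would be no reason to list it. Listing it suggests follow-up to 24 months after the last entry. The event-driven label and Protocol 9.4.1 give that reading some support, and under it 350 is enough. This stands as an account of how 350 may have arisen, and it makes the shortfall conditional. It does not rescue the stated power, because the SAP excludes events after day 730. Once the cap applies, every per-annum reading tried falls below 80%.

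A second reply is that the bullet without a unit may be shorthand for the annual rate given in the next paragraph. That is fair: it is an incomplete bullet, not a proven contradiction.

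A third reply is size. A control risk of about 36.3% instead of 35% would close the gap. Enrollment is described as approximate. With 25 months per patient (the visit window allows one extra month), N falls to about 352 to 353. This bears on how much the point matters. The extra month does not help the primary analysis, which stops at day 730.

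A reader might go further and infer that the annual unit is a slip, that 10% over 24 months was the true input, and that 350 can stand once the wording is changed. The documents do not support that. The uncapped calculation with 35% as a hazard gives 349 to 351 at 10% per annum. Nor does 10% over 24 months secure 350 under every convention: simple inflation of the 331 patients needed without loss, 331/0.9, gives 368. A reader might also set 10% against 19% as the losses the trial would see. But 19% is loss in the absence of events; in the model above about 12 to 13% are lost before an event by two years.

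**Conclusion.** The concern holds in a limited, conditional form. With 35% one-year risk, a hazard ratio of 1.0, 10% loss per annum, a constant hazard and the 730-day cap, 350 patients narrowly miss the stated target. The shortfall is 5 to 6 expected events and 1.1 to 1.3 power points, or 10 to 12 patients on the minimum. The 191-event trigger is then more likely to be missed than met.

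It would be wrong to say without qualification that the design is underpowered, since power at 350 is about 80% or higher if follow-up is uncapped. It would also be wrong to say which loss input was used. The two-year limit is the better supported calendar, and it is the one the SAP analyses. These figures take the SAP's 730-day window; the one-year window in Protocol 9.4.2 is a separate matter and is not used here.

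**What to change.** In Protocol 9.4.4 and SAP 4:

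- Give the loss rate one time unit, the same in the bullet and in the closing paragraph.
- State that the calculation uses 24 months per patient, to match the 730-day cap.
- If 10% per annum is the assumption, restate the figures for 350 patients as about 185 expected events and about 79% power, and stop calling 350 the minimum for 80%.
- Change the loss wording to 10% over 24 months only if the sponsor's own calculation shows that this was the input.

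No extra enrolment is needed. The cost is one sentence in each document and a slightly less favourable stated power.
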